1. SYNOPSIS

NAME OF COMPANY Sarepta Therapeutics, Inc. [name] [contact]	NAME OF FINISHED PRODUCT Eteplirsen Injection
	NAME OF ACTIVE INGREDIENT Eteplirsen
TITLE: An Open-Label Safety, Tolerability, and Efficacy Study of Eteplirsen in Patients with Duchenne Muscular Dystrophy Who Have Completed Study 4658-102	
Study Number: 4658-102-OLE	
Phase of Study: Phase 2	
INVESTIGATOR STUDY SITES: This multicenter study will be conducted at approximately 4 sites in Europe.	
OBJECTIVES: Primary Objective 
• To evaluate the ongoing safety and tolerability of additional treatment with eteplirsen administered once weekly by intravenous (IV) infusion in male Duchenne muscular dystrophy (DMD) patients who have successfully completed the 96-week eteplirsen study: Study 4658-102. Exploratory Objective 
• CCI	
METHODOLOGY: This is an open-label extension (OLE) study to assess the ongoing safety, tolerability, and efficacy of weekly IV infusions of eteplirsen in DMD patients who have successfully completed Study 4658-102. Patients will have the opportunity to enroll in this study during the last visit of Study 4658-102 (Week 96). After enrollment, patients will receive the CCI mg/kg dose of eteplirsen while in the study. The period from Baseline through Week 284 will be considered the “Treatment Period.” Week 284 will be followed by a 4-week Safety Follow-up Period. Patients may transition to commercially available product if commercially available eteplirsen is available at any time during the study, without undergoing the Safety Follow-up Period. Home infusion of the study drug may be available. Safety and efficacy assessments will be performed at scheduled visits; adverse events (AEs), concomitant medications, and concomitant therapies will be continuously monitored. The CCI (CCI) will be administered to all patients; a revised version will be used for patients \leq 3 years of age. If review of data from this OLE study suggests that continued treatment with eteplirsen is warranted, this study may be extended by protocol amendment, or patients may transition to commercially available product if commercially available eteplirsen is available.	
NUMBER OF PATIENTS: Up to 15 patients will be enrolled in this study.	

NAME OF COMPANY	NAME OF FINISHED PRODUCT
Sarepta Therapeutics, Inc. [name] [contact]	Eteplirsen Injection
NAME OF ACTIVE INGREDIENT	Eteplirsen

INCLUSION/EXCLUSION CRITERIA:

Inclusion Criteria:

A patient must meet all of the following criteria to be eligible to participate in this study:

1. Patient has successfully completed 96 weeks of treatment in Study 4658-102.
2. Parent(s) or legal guardian(s) who is/are able to understand and comply with the study requirements.
3. Patient and/or their parent(s)/legal guardian(s) are willing and able to provide signed informed consent.

Exclusion Criteria

A patient who meets the following criterion will be excluded from this study:

1. Patient has a prior or ongoing medical condition that, in the Investigator's opinion, could adversely affect the safety of the patient, or make it unlikely that the course of treatment or follow-up would be completed, or impair the assessment of study results.

DOSE/ROUTE/REGIMEN(TEST ARTICLE):

The dose of eteplirsen will be calculated based on the most recent patient weight obtained at the site prior to the current visit. Please refer to the study-specific Pharmacy Manual for information on preparation and administration of eteplirsen.

Patients will receive the **cc** mg/kg dose of eteplirsen for up to 284 weeks while in the study.

CCI

It is recommended that a topical anesthetic cream (eg, lidocaine 2.5%, prilocaine 2.5%, or LMX4 cream) be applied to the infusion site prior to each administration of study drug. Patients should be observed for possible reactions to the infusion for at least 1 hour after each infusion. Home infusion of the study drug may be available.

NAME OF COMPANY Sarepta Therapeutics, Inc. [name] [contact]	NAME OF FINISHED PRODUCT Eteplirsen Injection
	NAME OF ACTIVE INGREDIENT Eteplirsen
REFERENCE TREATMENT: None	
CRITERIA FOR EVALUATION:	
Safety and Tolerability The safety and tolerability of eteplirsen will be assessed through a review and evaluation of: 
• The frequency and severity of AEs, serious adverse events (SAEs), and discontinuation of treatment due to AEs• Deaths due to AEs• Adverse events of special interest, including infusion-related reactions, hypersensitivity, and renal events• Laboratory testing, including hematology, coagulation, serum chemistry, and urinalysis• Cardiac function assessments, including electrocardiogram (ECG)• Vital signs• Physical examinations	
Efficacy The efficacy of eteplirsen will be assessed by evaluating the change in NSAA scores from Baseline to the end of Week 144, Week 192, and Week 284.	
STATISTICAL METHODS:	
Sample Size As this study is an OLE study of Study 4658-102, the sample size will be predicated on the sample size of Study 4658-102.	
Safety Analyses Adverse events will be coded using the Medical Dictionary for Regulatory Activities (MedDRA) Version 20.1 or higher. An AE will be defined as a treatment-emergent adverse event (TEAE) if it developed or worsened in the period from the first dose of study drug to 28 days after the last dose of study drug. A treatment-related TEAE will be defined as a TEAE that the Investigator considered related to the study treatment.	

NAME OF COMPANY Sarepta Therapeutics, Inc. [name] [contact]	NAME OF FINISHED PRODUCT Eteplirsen Injection
	NAME OF ACTIVE INGREDIENT Eteplirsen

Congenital anomaly/birth defect: A congenital anomaly/birth defect that occurs in the offspring of a patient exposed to the investigational product.Important medical event: An AE that may not result in death, be life-threatening, or require hospitalization may be considered an SAE when, based upon appropriate medical judgment, the event may jeopardize the patient and may require medical or surgical intervention to prevent one of the outcomes listed above.	

For TEAEs, treatment-related TEAEs, and treatment-emergent SAEs, the number and percentage of patients reporting AEs will be summarized according to MedDRA system organ class (SOC) and preferred term (PT) for each age cohort and for the overall study. Multiple occurrences of the same AE at the same PT level in the same patient will be counted only once in the calculation of the number and percentage of patients reporting AEs for each PT. In addition, for TEAEs and treatment-related TEAEs, the number and percentage of patients reporting AEs will be summarized, according to MedDRA SOC and PT, by maximum severity for each age cohort and for the overall study. In this summary, if a patient has experienced multiple episodes of the same event with different severities, the event with the maximum severity will be used.
 
Safety laboratory tests, vital signs, and ECG parameters will be summarized by age cohort and for the overall study using the number and percentage of patients who met the criteria of predefined potentially clinically significant values, as appropriate.
	

CCI
 
[REDACTED]
 
[REDACTED]
	

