5.5. Benefit and Risk Assessment

Details about the known and expected benefits and risks of, and expected AEs associated with, eteplirsen treatment are provided in the eteplirsen Investigator's Brochure.

Eteplirsen has been granted accelerated approval in the US by the Food and Drug Administration. This was based on the observation of dystrophin production in some patients and the safety experience in patients with DMD participating in clinical trials, who were 4 years of age or older, which includes the age range specified for this study. Patients have also used commercially available eteplirsen since the approval in September 2016.

To date, eteplirsen has been well tolerated, with low rates of serious or severe AEs. No major safety risk has been identified in patients dosed with eteplirsen, including patients dosed with up to 50 mg/kg once weekly for more than 4 years.

Risks with eteplirsen include infusion-related reactions, hypersensitivity reactions, and potential renal toxicities including proteinuria or decreased renal function. These events have been seen in prior experience with eteplirsen with lower doses and are usually mild and resolve without clinical or pharmaceutical treatment. The use of higher doses of eteplirsen in this protocol could lead to more frequent or more severe reactions than seen with lower doses. Regularly scheduled review by a Safety Review Committee during the open-label period and a Data Monitoring Committee (DMC) during the double-blind period will look at aggregate unblinded data to determine the relative risk-benefit of continuing the dose or the study. Investigators are allowed to withhold dosing and must discuss such actions with the Medical Monitor. Further details on the safety of eteplirsen can be found in the Investigator's Brochure.

Based on the mechanism of action of eteplirsen and the benefit of eteplirsen treatment in DMD patients with mutations amenable to skipping exon 51, it is expected that patients in Study 4658-102-OLE may derive a clinical benefit from treatment with a higher dose of eteplirsen.

Taken together, these considerations support that patients participating in Study 4658-102-OLE will not be exposed to undue risk and may potentially experience some clinical benefit.

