7.3. Study Endpoints

7.3.1. Safety and Tolerability Endpoints

- Incidence of AEs, serious adverse events (SAEs), and discontinuation from treatment due to AEs
- Incidence of deaths due to AEs
- Incidence of adverse events of special interest (AESIs), including infusion-related reactions, hypersensitivity, and renal events
- Clinically significant laboratory testing, including hematology, coagulation, serum chemistry, and urinalysis
- Clinically significant cardiac function assessments, including electrocardiogram (ECG)
- Clinically significant vital signs
- Clinically significant physical examinations

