11.3.9. Adverse Events of Special Interest

Adverse events of special interest are AEs (serious or nonserious) that are of special scientific and/or medical interest, for which ongoing and rapid communication by the Investigator to the sponsor is appropriate.

The AESIs for this study are listed below. All AESIs should be reported as AEs to the sponsor within 24 hours of awareness irrespective of adverse event seriousness. This includes the events below that are based on lab abnormalities, which should be translated to an appropriate adverse event term at the time of reporting.

Nephrotoxicity

- Proteinuria $> 500 \text{ mg/24 hr}$
- eGFR $< 60 \text{ ml/min/1.73 m}^2$

Hepatotoxicity

- GGT or GLDH $> 8 \times \text{ULN}$
- GGT or GLDH $> 5 \times \text{ULN}$ for more than 2 weeks
- GGT or GLDH $> 3 \times \text{ULN}$ and (total bilirubin $> 2 \times \text{ULN}$ or international normalized ratio > 1.5)
- GGT or GLDH $> 3 \times \text{ULN}$ with the appearance of the following signs or symptoms: fatigue, vomiting, right upper quadrant pain or tenderness, fever, rash, and/or eosinophilia ($> 5\%$)

Hypersensitivity

- Anaphylaxis, anaphylactoid reaction, or angioedema
- Any severe allergic reaction
- Any severe complement mediated, inflammation event (eg, acute kidney injury, arteritis, myocarditis, pneumonitis)

Thrombocytopenia

- Platelet count $< 75,000/\text{mm}^3$

Infusion-related reactions

- All infusion related reactions considered severe (see Section 11.3.4), occurring within 24 hours of the eteplirsen infusion, should be reported to the Sponsor within 24 hours of awareness.

Infusion-related reactions may include headache, vomiting, diarrhoea, pyrexia, abdominal pain, upper, flushing and nausea. There may be pain at the site of the infusion as well as bruising surrounding the infusion site. Infections are also possible at the site of the infusion.

Rhabdomyolysis

- Rhabdomyolysis adverse events regardless of severity

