11.4. Recording Adverse Events

All AEs/SAEs experienced from the time of signed informed consent to the last follow-up will be recorded within each patient's eCRF. Information to be recorded should include: a concise description of the event; date and time of event onset and resolution; determination of seriousness, severity, corrective treatment, outcome, and relationship to IP or study procedure or underlying disease; and any action taken will be recorded. Resolution occurs when the patient has returned to his Baseline state of health or further improvement or worsening of the event is not expected.

Whenever possible, a diagnosis will be recorded as an AE, rather than symptoms or isolated laboratory abnormalities related to that diagnosis. Several symptoms or laboratory results that are related to the same diagnosis can thus be part of the same AE. A medical or surgical procedure is not an AE; rather the condition leading to the procedure should be recorded as the AE. Similarly, death is not an AE, but is rather the outcome of the AE(s) that resulted in death. If the AE(s) leading to death are not known, then death must be reported as an AE. All AEs will be followed until the resolution of AE, completion of the patient's study participation, or study termination, whichever occurs first. SAEs will be followed until resolution or until the condition stabilizes or returns to Baseline status.

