13.7.1. Adverse Events

Adverse events will be coded using the Medical Dictionary for Regulatory Activities (MedDRA) Version 20.1 or higher.

All AEs will be classified as either TEAEs or non-TEAEs. An AE will be considered a TEAE if it occurs at or after the start of study drug administration and within 4 weeks after the last study drug administration. An AE that does not meet the TEAE definition will be classified as a non-TEAE.

Treatment-emergent AEs will be summarized using the number and percentage of patients reporting AEs, by MedDRA system organ class (SOC) and preferred term (PT), for each dose

level and for the overall study population. The ordering of AEs will be based on the AE rate in the overall study population.

In general, summaries will have AEs categorized into all TEAEs and treatment-related TEAEs. Treatment-related TEAEs will be defined as those that the Investigator considers to be related to the study treatment (Section 11.3.1).

The following summary tables will be produced:

- TEAEs
- TEAEs by severity
- Treatment-related TEAEs
- Treatment-related TEAEs by severity
- SAEs
- AESIs
- AEs leading to study treatment discontinuation
- AEs leading to study withdrawal
- Deaths

The following listings will be produced:

- All TEAEs
- Non-TEAEs
- SAEs
- AESIs
- AEs leading to study treatment discontinuation
- AEs leading to study withdrawal
- Deaths and reasons for deaths

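### The adverse event tables count patients only, so they cannot show recurrence within a boy or frequency per infusion; one added descriptive table would

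*Combined protocol and SAP*

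**What the plan says.** The Synopsis (Statistical Methods, Safety Analyses) sets the counting rule: "Multiple occurrences of the same AE at the same PT level in the same patient will be counted only once". The sentence goes on to limit the rule to the number and percentage of patients reporting each preferred term. For the severity tables the Synopsis adds that "if a patient has experienced multiple episodes of the same event with different severities, the event with the maximum severity will be used".

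Section 13.7.1 uses the same unit: "Treatment-emergent AEs will be summarized using the number and percentage of patients reporting AEs". It names nine summary tables, covering TEAEs and treatment-related TEAEs (each also by severity), SAEs, AESIs, AEs leading to treatment discontinuation, AEs leading to study withdrawal, and deaths. None is described as counting episodes or as using infusions or time as denominator. The tables are ordered by an AE rate that is not defined.

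On what is to be assessed, the Synopsis criterion is "The frequency and severity of AEs, serious adverse events (SAEs), and discontinuation of treatment due to AEs", while the endpoint in Section 7.3.1 is "Incidence of AEs, serious adverse events (SAEs), and discontinuation from treatment due to AEs". Section 5.5 says that higher doses "could lead to more frequent or more severe reactions than seen with lower doses".

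In Section 11.3.9 the infusion-reaction AESI covers reactions judged severe and "occurring within 24 hours of the eteplirsen infusion". Under footnote h of Table 2, the infusion-reaction form is tied to that AESI.

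Most of the data for a per-infusion summary are already planned. Section 11.4 records the "date and time of event onset and resolution", Section 13.6 summarises the number of infusions received, and Sections 13.7 and 13.7.1 list all TEAEs.

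**The concern.** This is an uncontrolled study of weekly infusions lasting more than five years, with infusion-related reactions among its listed endpoints. Tolerability of such a regimen depends on how often a reaction comes back as well as on whether a boy ever has one. A count-once table records a boy who vomits after one infusion and a boy who vomits after 100 in the same way.

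Section 5.5 describes infusion reactions, hypersensitivity and renal events in earlier experience at lower doses as usually mild. A mild infusion reaction falls outside the AESI definition in Section 11.3.9. In the tables it appears only as a count-once entry, spread over separate preferred terms such as vomiting, flushing, nausea or headache. A pattern of mild reactions that persist or become more frequent would therefore be visible only to someone reading the listings line by line.

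**Working it through.** The plan states no AE rate, episode count or power, so there is no figure to reproduce. The calculations below show what the patient count can and cannot separate.

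**Inputs**
- Patients: up to 15 (Section 8.1).
- Infusions per boy: up to 283, weekly in Weeks 1 to 283 (Table 2, footnote a). Section 9.2 says up to 284 weeks. The difference is immaterial: 15 × 283 = 4,245 infusions, 15 × 284 = 4,260.
- Risk of a reaction per infusion, p: not given in the documents. A range is assumed.

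**Recurrence (needs no assumption about p)**
- Three boys with one episode each: table entry 3/15 = 20%; rate 3/4,245 × 100 = 0.07 episodes per 100 infusions.
- Three boys with 100 episodes each: table entry 3/15 = 20%; rate 300/4,245 × 100 = 7.07 episodes per 100 infusions.

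The entry is the same for a hundredfold difference in episodes.

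**Saturation (assumes the same p in every boy, independent infusions, full exposure)**

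Expected boys counted = 15 × [1 − (1 − p)^283]. Expected infusions with a reaction = 4,245 × p.

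| p doubles | Boys counted, of 15 | Ratio | Infusions with a reaction |
|---|---|---|---|
| 0.05% to 0.1% | 2.0 to 3.7 | 1.87 | 2.1 to 4.2 |
| 0.1% to 0.2% | 3.7 to 6.5 | 1.75 | 4.2 to 8.5 |
| 0.5% to 1% | 11.4 to 14.1 | 1.24 | 21.2 to 42.5 |
| 1% to 2% | 14.1 to 15.0 | 1.06 | 42.5 to 84.9 |
| 2% to 4% | 14.95 to 15.0 | 1.00 | 84.9 to 169.8 |

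For rare reactions the patient count nearly doubles with the risk. From about 0.5–1% per infusion it flattens.

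**Sensitivity to clustering**

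Let each boy's risk follow a Beta(a, b) distribution with mean p = a/(a + b). Expected boys counted = 15 × [1 − B(a, b + 283)/B(a, b)], where B is the beta function. A smaller a + b means stronger clustering in a few boys; the values of a + b are assumed. For p from 2% to 4%:
- a + b = 1: 1.8 to 3.3 boys
- a + b = 5: 5.1 to 8.5 boys
- a + b = 20: 10.0 to 13.4 boys

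With clustering, then, the patient count does respond to a doubling at these rates. It still does not show how many episodes each affected boy has.

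**The case against.** The strongest reply is that nothing in the tables is wrong. Counting a patient once per term is the correct definition of a patient count, and the rule says that this is its purpose. Section 13.2 points to Section 7.3 for the endpoints, and Section 7.3.1 speaks of incidence, which the tables measure. Tables of treatment-related TEAEs, of severity and of AESIs also exist, so the severity half of the risk named in Section 5.5 is covered. With at most 15 boys, recurrence can be read from the listings. Section 13.1 leaves details to a SAP that is not in the text reviewed, and Section 13.9 allows additional analyses.

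Most of this stands, and it rules out two stronger readings. A reader might infer that the tables cannot measure the plan's own safety criterion. That holds only if the word frequency in the Synopsis means episodes, and Section 7.3.1 supports the patient-based reading. A reader might also infer from the saturation table that a doubling of risk would be invisible. That requires frequent reactions with equal risk in every boy and independent infusions; it fails for rare events and under clustering.

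Section 5.5 is also limited support. It refers to a double-blind period that this open-label study does not have, and its comparison with lower doses cannot be made within a study that has no reference treatment.

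What the reply does not answer is recurrence. Listings hold the events but give no rate or trend, and the text reviewed does not commit to a table that does. The AESI table is restricted to severe infusion reactions.

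**Conclusion.** A cheap improvement is missing; the analysis as planned is not in error. The described tables are valid for incidence but carry no information on recurrence within a boy or on frequency per infusion. The recurrence example (20% in both cases, against 0.07 and 7.07 episodes per 100 infusions) rests only on 15 boys and full exposure. The flattening of the patient count from about 0.5–1% per infusion rests on an assumed risk that is similar between boys, and should not be presented as a general property of the tables. The gap matters most for mild, repeated infusion reactions, which the AESI definition leaves out. The SAP may already close it; the text reviewed does not show that.

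**What to change.** Keep the count-once tables. Add to Section 13.7.1 and the SAP one descriptive table, for the infusion-reaction terms listed in Section 11.3.9 at any severity and for treatment-related TEAEs, giving:
- the number of episodes;
- the number and percentage of infusions followed by at least one such event within 24 hours, or on the same or next calendar day if infusion clock times are not recorded (the text does not say that they are);
- both per boy, overall and by study period, with infusions received as denominator.

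Define AE rate in Section 13.7.1 and state whether frequency in the Synopsis means patients or episodes.

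It would be tempting to compare the share of onsets in the 24 hours after an infusion with the one seventh expected from a weekly cycle. This is not advised: AEs are asked about at infusion visits, so reported onsets may cluster there, and Section 9.2 allows a window of ±3 days around each dose.

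The cost is SAP wording and one more table, linking AE onset to dosing records. No new visit or procedure is needed. The table will still be affected by visit-linked reporting, and without a control arm any comparison with lower doses stays external.

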2. SCHEDE OF EVENTS

The schedule of study events is presented in [Table 2](#).

Evaluations should be performed in the order in which they appear below.

On infusion days, all evaluations should be performed prior to infusion, except vital signs, which should be assessed before and after the infusion.

Table 2: Schedule of Events

Visit/Week	BL	Weekly Visits																								284 (End of Study ^k)	288 (Safety Follow-up ^l)	
		1 ^a	12 ^a	24	36	48	60	72	84	96	108	120	132	144	156	168	180	192	204	216	228	240	252	264	276			
Informed Consent	X																											
Inclusion/Exclusion Eligibility	X																											
Safety Laboratory Assessments ^b	X ^c		X	X	X	X	X	X	X	X	X	X	X	X	X	X	X	X	X	X	X	X	X	X	X	X	X	
Vital Signs ^d																												X
Weight																												
Urine dipstick testing																												
Renal function blood tests ^m	X	X	X	X	X	X	X	X	X	X	X	X	X	X	X	X	X	X	X	X	X	X	X	X	X	X		
Quantitative urine analysis ⁿ	X	X	X	X	X	X	X	X	X	X	X	X	X	X	X	X	X	X	X	X	X	X	X	X	X	X		
Physical Exam (including height & ulnar length) ^e	X ^c		X	X	X	X	X	X	X	X	X	X	X	X	X	X	X	X	X	X	X	X	X	X	X	X		
CCI ^{i,o}	X ^{c,j}									X																		X
ECG ^o	X ^c		X	X	X	X	X	X	X	X	X	X	X	X	X	X	X	X	X	X	X	X	X	X	X	X		
Eteplirsen Infusion ^f																												
Con Meds/Therapies Assessment																												
AE Assessment ^{g,h,i}																												

AE = adverse event; AESI = adverse event of special interest; BL = Baseline; con med = concomitant medication; ECG = electrocardiogram; EOS = end-of-study; ICF = informed consent form; CCIⁱ = CCI^j; OLE = open-label extension.

^a For Weeks 1 to 283, visits will include vital signs, weight, eteplirsen infusion, and assessments of con meds/therapies and AEs. Additionally, the Week 12 visit and visits every 12 weeks subsequently will also include safety labs, ECG, and physical exam (including height and ulnar length).

^b Safety laboratory assessments will include hematology tests (including platelets), coagulation studies, serum chemistries (including liver function).

^c These assessments will not be performed at Baseline if performed at Week 96 of Study 4658-102.

- d. Vital signs will include blood pressure, heart rate, respiration, and axillary temperature. On infusion days, vital signs will be measured within 60 minutes prior to infusion and 30 minutes (\pm 10 minutes) after the end of the infusion. All assessments will be performed after patients have remained calm for 5 minutes. Pulse rate and respiratory rate should be measured over 1 minute.
- e. Height and ulnar length will be measured as part of every physical examination. The examination will also include general appearance; head, ears, eyes, nose, throat; heart; lungs; chest; abdomen; skin; lymph nodes; musculoskeletal system; and neurological systems.
- f. Patients will receive ~~cc~~ mg/kg of eteplirsen once a week over 35-60 minutes, and will be observed for at least 1 hour after each infusion. It is recommended that a topical anesthetic cream (eg, lidocaine 2.5%, prilocaine 2.5%, or LMX4 cream) be applied to the injection site prior to each infusion.

Once a patient begins receiving weekly eteplirsen infusions at satellite sites, all subsequent infusions should be administered at the patient's satellite site unless otherwise indicated and approved by the Medical Monitor. Patients may receive home infusions starting at Week 1. Note that an implanted venous access port may be inserted for eteplirsen administration at the discretion of the Investigator.

- g. AEs should be recorded at all visits. Spontaneously reported AEs occurring within 28 days after the last dose of eteplirsen will also be recorded.
- h. In the event that a patient experiences an AESI of infusion-related reaction, an infusion-related reaction case report form should be completed.
- i. Special situations (eg, overdose, medication error, accidental/occupational exposure) should be monitored and recorded.
- j. For patients aged \leq 3 years the revised ~~CCI~~ will be used. For patients aged >3 age-appropriate items from the ~~CCI~~ (Mercuri 2016) should be performed.
- k. Patients who are withdrawn from the study early will be asked to complete all end-of-study (EOS) assessments prior to withdrawal and within 28 days of their last eteplirsen infusion, if possible, unless they have completed a physical exam and safety labs within 28 days of withdrawal.
- l. All patients will be asked to complete the Safety Follow-up visit 28 days after their last dose of eteplirsen. Patients may transition to commercially available product if commercially available eteplirsen is available.
- m. Renal function blood tests include creatinine, blood urea nitrogen, and serum cystatin C.
- n. Quantitative urine analysis includes KIM-1 and urinalysis (pH, specific gravity, protein, glucose, ketones, cytology, and hemoglobin).
- o. A 2-week window is allowed in the event the child is unable to complete this assessment at a given visit.

Note: Rollover Instructions:

- Subject is able to rollover within 1 week (7 calendar days) from main to OLE
 - Main study Week 96 study assessments will be used as Baseline assessments in OLE
 - No safety follow-up visit needed for main study
- Subject rolls over to OLE more than 7 days after conclusion of main study
 - All baseline assessments to be performed fresh for OLE study
 - No safety follow-up visit needed for main study if rollover/ICF for OLE occurs within 4 weeks of main study Week 96
 - If rollover/ICF occurs more than 4 weeks after Week 96 of main study, perform safety follow-up visit

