10.3.4.2. Safety Monitoring for Renal Function

Renal tests need to be monitored as specified in the Schedule of Events ([Table 2](#)). Patients with the following test results need to undergo repeat testing for confirmation of abnormal test results:

- Protein $\geq 2+$ (dipstick)
- Urine Protein to Creatinine Ratio $\geq 150\text{mg/g}$
- Urine Albumin to Creatinine Ratio $\geq 30\text{mg/g}$
- Serum Creatinine $\geq 0.3 \text{ mg/dL}$ above baseline
- Serum Creatinine $\geq 1.5 \times$ ULN
- Estimated glomerular filtration rate (eGFR) $\leq 60 \text{ ml/min}/1.73\text{m}^2$
- Red blood cells (RBCs) $> 1/\text{hpf}$
- Elevated Cystatin C $>$ ULN
- Elevated kidney injury molecule 1 $>$ ULN

Additional Investigations:

24-hour urine collection needs to be undertaken to quantify any proteinuria and glomerular filtration rate (GFR) changes indicated by confirmed results as above. Additional evaluations including nephrology consultation, renal US/CT/MRI, renal biopsy, may be performed at the discretion of the Investigator in consultation with the Sponsor Medical Monitor.

Stopping Rules for Renal Test Results:

In the event of laboratory results meeting the following criteria, **and the event is without an alternative explanation as discussed with the Sponsor Medical Monitor**, dosing of a patient with eteplirsen will be stopped permanently:

- Quantitative total urine protein measurement of $\geq 1 \text{ g}/24 \text{ hours}$
- Measured GFR (creatinine clearance) $\leq 45 \text{ mL/min}/1.73\text{m}^2$
- Gross hematuria
- Any RBC Casts
- Persistent microscopic hematuria $\geq 3 \text{ RBCs/hpf}$ for 3 consecutive weeks

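### For patients who roll over more than 7 days after Study 4658-102, Table 2 footnote c and the rollover instructions conflict on whether four Baseline assessments are repeated

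*Combined protocol and SAP*

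**What the plan says.** In Table 2 (protocol Section 2, Schedule of Events), four rows carry footnote c at Baseline: safety laboratory assessments, physical examination with height and ulnar length, the functional scale, and ECG. The footnote reads: "These assessments will not be performed at Baseline if performed at Week 96 of Study 4658-102". No interval is attached.

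The rollover instructions printed after the footnotes distinguish two cases.

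- Early entry, up to 7 calendar days after the main study. Here the rule is: "Main study Week 96 study assessments will be used as Baseline assessments in OLE".
- Late entry, beyond 7 days. Here the rule is: "All baseline assessments to be performed fresh for OLE study".

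The instructions also provide for entry more than 4 weeks after Week 96 and set no maximum gap. The row "Renal function blood tests" and the quantitative urine row have a Baseline entry without footnote c.

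Section 10.2.2 lists the Baseline assessments with neither the waiver nor the 7-day rule. Section 13.8 analyses the functional score as change from Baseline without saying which record is Baseline. Section 13.1 leaves statistical detail to a SAP, and no separate SAP text is included in the document available.

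**The concern.** Completing 96 weeks of treatment in Study 4658-102 is an entry criterion (Section 8.2), so nearly every enrollee is likely to have Week 96 assessments and so to meet footnote c's condition. For a late rollover, one instruction then says not to repeat the four assessments and the other says to repeat them. A coordinator working from the Baseline cell and its footnote would reuse Week 96; one working from the rollover instructions would measure again.

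The reference value matters in three places:

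- the change in functional score to Weeks 144, 192 and 284 (Section 13.8);
- the liver confirmation trigger, which uses twice Baseline when Baseline exceeds the upper limit of normal (Section 10.3.4.1);
- the investigator's judgment of clinically significant laboratory or ECG worsening, made against Baseline (Sections 10.3.5 and 10.3.6).

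If the older value is used, any change between Week 96 and entry to the extension is counted as change during the extension. If practice differs between sites, the summaries mix two definitions of Baseline.

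**Working it through.** The plan gives no figure to reproduce, since Section 13.3 states that there is no formal sample size calculation. The check compares the instructions case by case for the four rows marked c.

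| Gap after main study | Marked assessment done at Week 96? | Footnote c | Rollover instructions | Result |
|---|---|---|---|---|
| 7 days or less | Yes | Not repeated | Week 96 serves as Baseline | Agree |
| More than 7 days | Yes | Not repeated | Repeated | **Conflict** |
| More than 7 days | No | Waiver does not apply | Repeated | No conflict |

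The conflict is confined to the middle line.

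**Which Baseline-referenced rules depend on the marked rows**

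- Functional score: its row is marked, so it is affected.
- Liver confirmation trigger: footnote b puts liver function in the safety laboratory row, which is marked, so it is affected. The Baseline multiple applies only when Baseline was above the upper limit of normal.
- Laboratory worsening: affected for tests in the marked safety laboratory row that are not also in an unmarked row.
- ECG worsening: its row is marked, so it is affected.
- Creatinine at least 0.3 mg/dL "above baseline" (Section 10.3.4.2): not affected. Footnote m places creatinine in the renal blood test row, whose Baseline entry has no footnote c. For a late rollover, both that row and the rollover instructions call for a Baseline creatinine.
- Permanent laboratory stopping rules for liver, renal and platelet results (Sections 10.3.4.1, 10.3.4.2 and 10.3.4.4): not affected. They use multiples of the upper limit of normal, absolute values or clinical findings, and none refers to Baseline.

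**Size**

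Enrolment is up to 15 (Section 8.1). Let k be the number of late rollovers, which is not stated. With 15 enrolled, the affected share is k/15:

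- k = 0: 0%
- k = 1: 1/15 = 6.7%
- k = 15: 100%

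The documents give no basis for choosing a value in this range.

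**The case against.** The strongest reply is that the rollover instructions are the more specific text, stand under the same table and plainly state the intended design. Read together, they qualify footnote c, and only a cross-reference is missing. That is probably what was meant. The document does not say so, however, and a site following the footnote alone would skip assessments that the instructions require.

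It is also fair to say that the consequences are modest. The one explicit change-from-Baseline analysis is exploratory and descriptive, and the liver criterion prompts confirmation and closer follow-up rather than permanent stopping. Section 7.1 lets patients enrol at the Week 96 visit, so late rollover may be rare or absent. A Baseline definition may also exist in the SAP. All of this stands and limits the weight of the point.

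A reader might infer more than the documents support:

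- That nobody repeats the Baseline tests. This ignores the rollover instructions. Footnote c is also conditional on each assessment having been done, and the entry criterion requires completed treatment, not every Week 96 test.
- That each late patient has two recorded Baselines. There are two candidate instructions; following either gives one value.
- That the creatinine trigger has an outdated reference. The unmarked renal row rules this out.
- That changes while off drug are counted as treatment effect. The rollover instructions do not state treatment status during the gap, so this is an inference.

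**Conclusion.** The inconsistency is real and narrow. For patients who enter more than 7 days after Study 4658-102 and had the marked assessments at Week 96, two instructions under the same table cannot both be followed for four assessments, and nothing else in the document settles which applies. It should be corrected, because it determines the reference value for the functional score, the liver confirmation trigger and judgments of laboratory and ECG worsening in a study of at most 15 patients. The number of patients affected is unknown, from 0 to 15, and no size of bias can be derived from the documents. Sample size, power and error rates are not involved. The conclusion rests on reading footnote c as written. If the sponsor confirms that the rollover instructions override it and that sites work that way, only the wording and the Baseline definition remain to be put right.

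**What to change.** Reconcile footnote c with the rollover instructions. One way is to make the footnote apply only to patients who roll over within 7 calendar days and to refer to the rollover instructions for everyone else. Add the same reference to Section 10.2.2. State in Section 13 or the SAP which record is the analysis Baseline for late rollovers, and list the patients concerned with the length of their gap. If any have already enrolled, record which Baseline each site used.

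The cost is one clause, one cross-reference, one definition and a short listing. Tying the footnote to the 7-day condition adds no procedure, because the rollover instructions already require the repeat assessments.
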